#### 4.2 Part 1: Dose De-Escalation

A total of 6 to 18 patients may be evaluated in Part 1 depending on the frequency of DLTs and the need for dose reductions. A 3+3 dose de-escalation design will be used to determine the recommended phase two dose while ensuring the safety and tolerability of the treatment. In this trial, the dose determined to be the maximum tolerated dose will be the recommended phase two dose and will be utilized in the cohort expansion. The study may test the possibility of three dose levels of itacitinib as described in Table 1.

**Table 1: Dose de-escalation Schedule**

	Itacitinib Dose
Dose Level 1 (starting dose)	200 mg daily, days 1-28
Dose Level -1	100 mg daily, days 1-28
Dose Level -2	100 mg every other day, days 1-28

Eligible subjects will be accrued in cohorts of 3 to 6 subjects per dose level starting at Dose Level 1. Three eligible subjects will be enrolled at a time and additional subjects will not be accrued until all three subjects have completed the defined DLT evaluation period and DSMC approval has been granted. If necessary, dose de-escalation will occur as described in Table 2 until DLT stopping rules are met or the lowest dose level is reached. The RP2D will be defined as the dose level at which less than one-third of subjects in a cohort experience a DLT.

**Table 2: 3+3 Dose de-escalation design**

Number of patients with DLT at a given dose level	De-escalation Rules
0 out of 3	Enroll 3 patients at the same dose level
1 out of 3	Enter 3 more patients at the same dose level 
 
If 1 out of 6 patients experiences a DLT, identify the dose level as the RP2D.
 

	
 
If <math>\geq 2</math> out of 6 patients experience a DLT, this dose level exceeds the MTD. Enroll 3 patients at the next lower dose level (if available).
 

$\geq 2$ of 3	This dose level exceeds the MTD. Enroll 3 patients at the next lower dose level (if available).
In order for a dose level to be declared the RP2D, 6 patients must be treated at that dose level with $\leq 1$ DLT observed.	

Treatment will initiate at an itacitinib oral dose of 200 mg daily (Cohort 1). If zero or one out of three patients have a dose-limiting toxicity (DLT), three additional patients will be accrued to Cohort 1. If a DLT occurs in one-third or more of the total cohort, cohort de-escalation will be required and three patients will be accrued to Cohort -1. If  $\geq$  two DLTs occur in the first three subjects in Cohort -1, three patients will be accrued at the Cohort -2 dose level with the same safety parameters. If six patients are ultimately treated at dose Cohort -2 and  $\geq$  two DLTs occur, the trial will be stopped and the combination will be deemed unsafe. The dose level in which  $\leq$  one patient out of six experiences a DLT (as defined in Section 4.3), in accordance to the 3+3 de-escalation rules (as described in Table 2), will be declared the RP2D.

Subjects must have received  $\geq 60\%$  of planned INCB039110 (21 doses) and ECP treatments (4 treatments) during the DLT observation period to be evaluable for dose tolerability. Patients who miss  $> 40\%$  of planned itacitinib doses or ECP treatments within the DLT evaluation period for any reason other than for the management of treatment-related toxicities, will not be evaluable and will be replaced.

If a subject experiences a DLT, the toxicity should be managed per Section 7. The subject may remain on study therapy if deriving clinical benefit as assessed by the treating investigator.

**Review and approval from the primary medical monitor and DSMC are required prior to all cohort expansions and dose escalations.**

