## 4 STUDY DESIGN

### 4.1 Description

This is an open-label, Phase II trial designed to assess the recommended phase 2 dose (RP2D) of itacitinib in combination ECP and efficacy of the combination after 24 weeks of therapy. The trial will consist of two parts: Part One will assess the RP2D. For dose-finding purposes, the DLT evaluation period will be defined as the time from the first dose of itacitinib lead-in (7-day lead-in) to the last day of cycle one combination therapy (cycle one day 28). Part Two will further describe and characterize the safety and efficacy of the regimen. The RP2D will be determined by a 3+3 dose de-escalation design. Should dose level one be deemed intolerable, enrollment will proceed at dose level -1. The RP2D will be affirmed according to the rules of the 3+3 dose de-escalation scheme (Section 4.2). Once an RP2D has been confirmed, Part 2 will open as an expansion cohort. Safety will be monitored during the trial as described in Section 11.3.

All eligible patients will begin study therapy with approximately a week lead-in of itacitinib monotherapy. After completing the itacitinib lead-in, combination treatment will begin in 28-day cycles. After eight weeks of combination therapy, patients will begin an ECP taper and continue on itacitinib for a total of 6 cycles. Patients achieving PR or better may

continue on itacitinib for up to 1 year. Patients will remain on study therapy as long as treatment discontinuation criteria are not met.

Prednisone dose (or prednisone equivalent) at  $\leq 0.25$  mg/kg/d for treatment of GVHD progressing or not sufficiently responding to study treatment will be allowed, at the discretion of the treating investigator and with approval of the PI, while the participant is on study treatment. Addition of prednisone dose (or prednisone equivalent) at  $\leq 0.25$  mg/kg/d will not be considered as failure of the primary endpoint. Prednisone doses (or prednisone equivalent) of  $> 0.25$  mg/kg/d but  $\leq 0.5$  mg/kg/d for more than 8 weeks or  $> 0.5$  mg/kg/d once will count as a failure of the primary endpoint, but the participant will be allowed to remain on the treatment period of the study. If the participant requires any systemic immunosuppression besides prednisone (i.e., ibrutinib, ruxolitinib, etc.), the participant will be withdrawn from study treatment but remain on study for follow-up.

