### 4.3 Dose Limiting Toxicity

For dose-finding purposes, the DLT evaluation period will be defined as the time from the first dose of itacitinib lead-in to the last day of cycle one combination therapy (cycle one day 28). The severity of AEs will be graded according to CTCAE v 5.0. For the purpose of dose-finding, any of the following AEs occurring during the DLT period, which are attributable (definite, probable, possible) to itacitinib or the combination of itacitinib and ECP will be classified as a DLT.

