### 6.1.1 ECP Taper

ECP will be given at a frequency of twice weekly for 8 weeks followed by a standard taper schedule as detailed below. Local institutional guidelines should be followed for the safe administration of ECP. Once a taper has initiated, investigators may consider increasing the frequency of ECP by one level if there is concern for GVHD progression and if prednisone (or prednisone equivalent) is not administered. This should be discussed with the PI first.

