**Table 4: Recommended ECP Schedule**

Week	ECP Schedule
1-8 (Start of therapy)	Twice weekly
9-16	Once weekly
17-24	Once every other week
25+ until physician discretion	Once monthly

During the taper, immune suppression will continue as described below.

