 Monitoring for infection will be performed at screening and for the duration of study therapy per institutional practice. Testing for cytomegalovirus and Epstein-Barr virus will be performed at screening. Prior test results obtained as part of standard of care before allo-HCT may be used for purposes of eligibility and tests do not need to be repeated. Routine infection monitoring should occur during the study as per institutional practice and include at a minimum PCR

testing on plasma for CMV and EBV and monitoring for fungal infections (i.e. Aspergillus). Additional monitoring should be performed during treatment if there is clinical suspicion of an infection.

 Screening assessment may be used if completed within 7 days prior to C1D1.

 Graft failure/chimerism should be performed on whole blood and should include: Chimerism, Post-Transplant and Chimerism, Post-Cell Sort, T cells.

 Participants will be closely monitored for any evidence of underlying disease relapse or recurrence during study therapy. These evaluations will be conducted in accordance with local institutional practices.

 To be completed prior to the physical exam at C1D1, C2D1, C3D1, C6D1, C8D1, C10D1, and EOT or PD visit.

 ECP will be given at a frequency of twice weekly for 8 weeks followed by a standard taper schedule as per study protocol. Refer to Table 4 for taper schedule.

 All patients will undergo 5 to 10 days of itacitinib monotherapy. The first ECP treatment will be considered C1D1. On days that the patient is being seen in clinic, itacitinib dosing does not need to be held prior to routine blood draws or for correlative studies.

 Patients may be on immune suppression at the time of study enrollment. On days that the patient is being seen in clinic, immunosuppressives should be held until after the blood draws if trying to achieve a therapeutic level. See Section 6.1.3.

 Correlative studies are only required during dose expansion. On days of drug administration, correlative blood samples should be drawn without regard to itacitinib dosing or ECP therapy. Patients should take itacitinib at their usual time. Blood will be drawn at screening, C1D1, the time of response, C7D1, and at EOT or progression, whichever occurs first.

 Only to be drawn from the first nine patients enrolled in Part 2, Dose Expansion.

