## **12.2 Population for analyses**

### **12.2.1 Part 1 DLT Evaluation**

Subjects must have received  $\geq 60\%$  of planned itacitinib doses (21 doses) and ECP treatments (4 treatments) during the DLT evaluation period or have had a DLT to be evaluable for dose tolerability.

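### Part 1 evaluability: 4 ECP treatments is 50% of the 8 planned, not the required 60%, and 21 itacitinib doses does not fit Dose Level -2

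*Combined protocol and SAP*

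**What the plan says.** Three places in the plan govern who counts in Part 1.

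- Section 4.2, in the text after Table 2, requires at least 60% "of planned INCB039110 (21 doses) and ECP treatments (4 treatments) during the DLT observation period to be evaluable for dose tolerability". The next sentence takes patients who miss more than 40% of planned "itacitinib doses or ECP treatments within the DLT evaluation period for any reason other than for the management of treatment-related toxicities" as not evaluable and replaces them.
- Section 12.2.1 requires at least 60% "of planned itacitinib doses (21 doses) and ECP treatments (4 treatments) during the DLT evaluation period or have had a DLT".
- Section 12.3 replaces Part 1 patients who fall below 60% compliance. It gives no counts and makes no exception for misses caused by toxicity.

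Section 4.1 defines the DLT period as "the time from the first dose of itacitinib lead-in (7-day lead-in) to the last day of cycle one combination therapy", and Section 4.3 repeats the definition without the lead-in length. Table 7, footnote 2, allows a lead-in of 5 to 10 days. On ECP, footnote 26 says "The first ECP treatment will be considered C1D1", and Section 6.1.1 says "ECP will be given at a frequency of twice weekly for 8 weeks followed by a standard taper schedule as detailed below". Table 1 sets daily itacitinib at Dose Levels 1 and -1, and every-other-day dosing at Dose Level -2.

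**The concern.** A percentage and a count that are meant to express the same threshold should agree. If they do not, a patient can be evaluable by one and replaced by the other, and the choice would be made with DLT data already in view.

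The choice matters because Table 2 requires 6 patients with no more than 1 DLT before a dose level becomes the RP2D. Under 12.2.1 a patient with a DLT is evaluable whatever the exposure, so every disputed patient is DLT-free. The looser count can therefore only add under-exposed patients without a DLT, which leans towards declaring the dose tolerable. The six patients at the RP2D are also carried into the first 16 of Part 2.

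**Working it through.** **ECP.** Inputs: two sessions a week (6.1.1, Table 4), first session on C1D1 (Table 7, footnote 26), DLT period ending on C1D28 (4.1, 4.3). The lead-in contains no ECP.

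- Planned sessions: 2 × 4 weeks = 8.
- Stated count: 4/8 = 50% received, 50% missed.
- 60% minimum: 0.60 × 8 = 4.8, so 5 sessions (5/8 = 62.5% received, 37.5% missed).

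Four would satisfy 60% with 6 planned sessions (4/6 = 66.7%), but nothing in the plan gives 6. Rounding 4.8 down to 4 breaks the at-least condition.

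**Itacitinib, daily levels.** With the 7-day lead-in of 4.1 the period is 7 + 28 = 35 days, and 0.60 × 35 = 21. The stated count is reproduced exactly. Over the lead-in range in Table 7 the period is 33 to 38 days, 21 is 63.6% to 55.3% of plan, and the 60% minimum runs from 20 to 23. The count is off by at most 2 doses.

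**Itacitinib, Dose Level -2.** The DLT period opens with a dose. The plan does not say whether the lead-in at this level is daily or every other day, so both readings are shown. In the second, cycle 1 contributes 14 doses and the lead-in one a day.

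| Lead-in (days) | Every other day throughout: planned | 60% minimum | 21 as % of plan | Daily lead-in, then every other day: planned | 60% minimum | 21 as % of plan |
|---|---|---|---|---|---|---|
| 5 | 17 | 11 | 123.5 | 19 | 12 | 110.5 |
| 6 | 17 | 11 | 123.5 | 20 | 12 | 105.0 |
| 7 | 18 | 11 | 116.7 | 21 | 13 | 100.0 |
| 8 | 18 | 11 | 116.7 | 22 | 14 | 95.5 |
| 9 | 19 | 12 | 110.5 | 23 | 14 | 91.3 |
| 10 | 19 | 12 | 110.5 | 24 | 15 | 87.5 |

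On the first reading a fully compliant DLT-free patient can never reach 21. On the second, 21 is between 88% and 111% of plan. Neither is 60%.

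**Effect on the dose decision.** Take one disputed, DLT-free patient in a cohort of six. If the other five have exactly 1 DLT, counting the disputed patient gives 1 of 6 (RP2D). Replacing that patient gives 2 of 6 (de-escalate) if the replacement has a DLT. With independent patients and a common DLT rate p:

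P(different decision | one disputed patient) = 5p(1 − p)⁴ × p = 5p²(1 − p)⁴

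| Assumed p | Probability |
|---|---|
| 0.10 | 5 × 0.01 × 0.6561 = 3.3% |
| 0.15 | 5 × 0.0225 × 0.5220 = 5.9% |
| 0.20 | 5 × 0.04 × 0.4096 = 8.2% |
| 0.30 | 5 × 0.09 × 0.2401 = 10.8% |

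The result is the same whichever of the six positions the disputed patient holds. Given that the cohort already has exactly 1 DLT, the probability is simply p. The plan gives no expected DLT rate for Part 1, so these values of p are illustrative.

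**The case against.** The strongest reply is that the percentage plainly governs. It appears in 4.2, 12.2.1 and 12.3, the replacement sentences use only percentages, and the counts are parenthetical. On that view 4 is just 4.8 rounded the wrong way, and the conflict touches one exact value in a run-in of 6 to 18 patients. Cohort expansions also need medical monitor and DSMC approval, where a borderline patient would probably be noticed. Dose Level -2 opens only after two failed levels, and there an unattainable 21 would likely be ignored in favour of 60%. The reversal probability is conditional on a disputed patient, nearly peaks at the upper end shown (about 11.0% at p = 1/3), and describes what any extra patient could do to a cohort with 1 DLT. It does not show that one reading gives the wrong RP2D.

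Much of this stands as to weight. The practical effect is probably small, and its unconditional size cannot be computed from the plan. It does not remove the error. Nothing in the plan says that the percentage overrides the count, and the wrong count stands in both the design section and the analysis-population section. The lead-in variation of at most 2 doses would not merit a comment by itself.

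**Conclusion.** The plan is wrong as written. The ECP count is 50% of planned sessions against a stated minimum of 60%. A DLT-free patient with exactly 4 of 8 sessions, the rest missed for reasons other than treatment-related toxicity, is both evaluable and to be replaced. The itacitinib count is right for daily dosing with the nominal lead-in and wrong at Dose Level -2, where the 60% minimum is 11 to 12 doses (every other day throughout) or 12 to 15 (daily lead-in).

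The ECP conclusion rests only on the schedule in the plan. The Dose Level -2 range depends on the unstated lead-in frequency, but 21 fails on either reading. The decision impact of 3.3% to 10.8% rests on an assumed DLT rate of 10% to 30% and on there being one disputed patient.

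A lesser mismatch sits beside this. Section 4.2 exempts doses missed to manage treatment-related toxicity, 12.2.1 exempts only a DLT, and 12.3 exempts neither for the 60% rule. It should rarely matter: Table 3 makes an adverse reaction leading to dose reduction or withdrawal a DLT (unless related to primary disease progression), and Section 7.1 restricts reductions in the DLT period. What remains is missed doses or sessions without a reduction, a withdrawal or another DLT.

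**What to change.** Delete the two parenthetical counts from 4.2 and 12.2.1, so that the percentage of planned treatment applies at every dose level and lead-in length. If an ECP count is kept, state 5 of 8. If an itacitinib count is kept, limit 21 to daily dosing with a 7-day lead-in.

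Then bring 4.2, 12.2.1 and 12.3 to a single evaluability and replacement rule. It should say whether a DLT-free patient who falls below 60% because of treatment-related toxicity is evaluable. The sponsor has to decide that point; the rest is editing.

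The cost is a few words in three sections. An occasional patient with exactly 4 ECP sessions would have to be replaced, which delays that cohort. The change should be made before such a patient arises.

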### 4.3 Dose Limiting Toxicity

For dose-finding purposes, the DLT evaluation period will be defined as the time from the first dose of itacitinib lead-in to the last day of cycle one combination therapy (cycle one day 28). The severity of AEs will be graded according to CTCAE v 5.0. For the purpose of dose-finding, any of the following AEs occurring during the DLT period, which are attributable (definite, probable, possible) to itacitinib or the combination of itacitinib and ECP will be classified as a DLT.

**Table 3: Definition of Dose-Limiting Toxicity**

Hematologic

 
Thrombocytopenia with grade <math>\geq 3</math> bleeding (i.e., requires hospitalization, transfusion of blood products, or other urgent medical intervention).
 

 
○ Transfusion of platelets to meet the requirements of the ECP procedure will not be considered a DLT.
 
● Platelet count <math>< 10 \times 10^9/L</math> lasting <math>> 3</math> days.
 
● Grade 4 neutropenia lasting <math>> 7</math> days.
 
● Grade 4 neutropenia that does not recover to <math>\leq</math> Grade 2 in <math>\leq 7</math> days after interrupting study drug.
 
● Grade <math>\geq 3</math> febrile neutropenia.
 
● Grade <math>\geq 3</math> anemia not explained by the underlying disease.
 

Non-hematologic

 
● Any Grade <math>\geq 4</math> non-hematologic toxicity
 
● Any Grade 3 non-hematologic toxicity except the following: 
 
○ Fatigue lasting <math>< 5</math> days.
 
○ Any non-Hy's law, liver abnormality that resolves <math>\leq 72</math> hours
 
○ Transient (<math>\leq 72</math> hours) abnormal laboratory values without associated clinically significant signs or symptoms.
 
○ Laboratory abnormalities deemed to be not clinically significant by the treating investigator.
 
○ Nausea, vomiting, and diarrhea adequately controlled with medical therapy within 48 hours.
 
○ Immune-related adverse events that improve to Grade <math>\leq 1</math> in <math>< 5</math> days by appropriate care or with corticosteroid therapy.
 
○ An event clearly associated with GVHD, GVHD progression, primary disease relapse, a concomitant medication, or comorbidity.
 
 
 
● Hy's Law cases: 
 
○ ALT or AST <math>> 3 \times</math> upper limit of normal (ULN) or <math>> 3 \times</math> ULN and doubled from baseline if <math>> ULN</math> at baseline and;
 
○ Total bilirubin <math>> 2 \times</math> ULN and;
 
○ Absence of cholestasis and;
 
○ No alternative etiology to explain the abnormalities.
 
 
 
● Any Grade 3 infection lasting more than 7 days in the absence of the primary disease progression.
 

General

 
● Any adverse reaction unrelated to the primary disease progression that leads to dose reduction or withdrawal
 

#### 4.4 Part 2: Dose Expansion

Upon identification of the Recommended Phase 2 Dose of itacitinib, an expansion cohort will open to the enrollment of 40 additional patients for further assessment of regimen safety and

efficacy. Enrollment will be conducted in two stages separated by an interim analysis. In the first stage of the dose-expansion study, 16 patients will be accrued. Of those 16 patients, 6 patients treated at the RP2D will be carried over from Part 1. In recognition of a potential accrual pause of at least 24 weeks if all 16 patients are required to complete six months of combination therapy, we will permit enrollment of an additional 3 patients after the first 10 eligible patients in the first stage of the dose-expansion study are enrolled if no more than 5 of 16 patients have experienced treatment failure (i.e., the addition of secondary systemic therapy or disease relapse or death) by the end of week 12 of treatment.

Once all 10 patients in Part 2 and the six patients treated at the RP2D in Part 1 have met treatment failure criteria or completed six months of combination therapy, whichever comes first, an interim analysis will be conducted to assess treatment efficacy. If  $\leq 7$  responses (CR or PR) in the first 16 enrolled patients are reported, the study will be stopped. Otherwise, the next stage of the expansion cohort will open to the enrollment of 30 additional patients.

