## 12 STATISTICAL CONSIDERATIONS

### 12.1 Sample Size Determination

#### Part 1

Part 1 has a maximum of 18 patients. Part 1 has a 3+3 dose de-escalation design with 3 doses and a maximum of 6 patients per dose.

#### Part 2

The sample size for Part 2 is 16-46 patients with 6 patients carried over from Part 1 at the RP2D. Simon’s optimal two-stage design will be used in Part 2. The primary outcome is the overall response rate (CR + PR) at 24 weeks. Withdrawal or progression prior to 24 weeks or missing 24-week assessment will be considered non-response. After the first 16 patients treated at the RP2D complete 24 weeks of therapy or meet treatment discontinuation criteria, enrollment will be put on hold and an interim analysis will be conducted. This study treatment will be considered promising if the overall response rate at 24 weeks is  $\geq 60\%$  and unacceptable if the overall response rate at 24 weeks is  $\leq 40\%$ . 50% is the reported best overall response rate of current first-line therapy with high-dose steroids. The null hypothesis that the true response rate is  $\leq 40\%$  will be tested against a one-sided alternative.

In the first stage of the dose-expansion study, 16 patients will be accrued and followed through the first 24 weeks of treatment. Of those 16 patients, 6 patients will be carried over from Part 1 at the RP2D. In recognition of a potential accrual pause of at least 24 weeks if all 16 patients are required to complete six months of combination therapy, we will permit enrollment of an additional 3 patients (20%) after the first 10 eligible patients in the first stage of the dose-expansion study are enrolled if no more than 5 of 16 patients have experienced treatment failure (i.e. addition of secondary systemic therapy or disease relapse or death) by the end of week 12 of treatment. If there are 7 or fewer responses in the first 16 patients enrolled, the study will be stopped. Otherwise, 30 additional patients

will be accrued for a total of 46. The null hypothesis will be rejected if 24 or more responses are observed in 46 patients. This design yields a type I error rate of 0.0486 and a power of 80% when the true response rate is  $\geq 60\%$ .

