## **12.3 Replacement of Participants**

### **Part 1**

Any participant who withdraws from the treatment before the completion of the DLT evaluation observation period for any reason other than a DLT may be replaced to ensure a minimum number of evaluable participants. Participants who do not maintain  $\geq 60\%$  study therapy compliance during the DLT evaluation period and participants who have a dose reduction due to concomitant medication use will be replaced.

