### **Part 2**

Participants will not be replaced unless they fail to begin study treatment.

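### The Simon stage 1 set is defined in two ways that part company once a Part 1 patient at the RP2D is replaced; under one of them early treatment failures can drop out of the primary endpoint

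*Combined protocol and SAP*

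**What the plan says.** **Who enters the Simon count.** Section 4.4 states: "Of those 16 patients, 6 patients treated at the RP2D will be carried over from Part 1". It triggers the interim analysis on those six plus the 10 new Part 2 patients, and Sections 4.4 and 4.5 set Part 2 enrolment at 40. Section 12.1 repeats the six, but times the interim differently: "After the first 16 patients treated at the RP2D complete 24 weeks of therapy" or meet discontinuation criteria. Its stopping rule reads: "If there are 7 or fewer responses in the first 16 patients enrolled, the study will be stopped". Section 12.4.1 and the study summary carry the same text, and the stopping rule in 4.4 also refers to the first 16 enrolled.

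**Part 1 replacement.** Under Section 12.3 a "participant who withdraws from the treatment before the completion of the DLT evaluation observation period for any reason other than a DLT may be replaced". Under Section 4.2, patients who miss more than 40% of itacitinib or ECP for reasons other than managing treatment-related toxicity "will not be evaluable and will be replaced". Sections 7.1 and 12.3 also replace patients whose dose is reduced because of a drug interaction.

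**Part 2 replacement and scoring.** Section 12.3 for Part 2: "Participants will not be replaced unless they fail to begin study treatment". Section 12.1 scores withdrawal, progression before week 24, or a missing week-24 assessment as non-response.

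**Efficacy population.** Section 12.2.3 makes patients evaluable for efficacy once they have had two weeks of combined treatment.

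**The concern.** Replacing non-evaluable patients is normal for a DLT denominator. The difficulty comes when that cohort is reused for efficacy. Some non-DLT exits are failures of the primary endpoint. Section 4.1 withdraws from treatment a patient who needs systemic immunosuppression other than prednisone, Section 6.7.1 lists relapse and death as treatment failure, and Section 9.3 stops therapy on progression. Table 3 exempts Grade 3 events clearly due to GVHD progression or relapse from DLT status. A patient with such an exit in the DLT window can be replaced.

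If seven or eight patients are then treated at the RP2D in Part 1, the sum 6 + 10 = 16 has no place for the seventh or eighth. The natural six are the DLT-evaluable ones, so six of 16 interim positions (38%) and six of 46 final positions would be filled after a selection that can depend on outcome. The text does not say which description governs. Left open, the choice would be made with outcomes already known, in an open-label single-arm trial.

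**Working it through.** **1. Inputs from Section 12.1.** Null rate 0.40, which "will be tested against a one-sided alternative"; alternative 0.60; stop at 7 or fewer of 16; reject at 24 or more of 46. The DLT window (Section 4.1) is a lead-in of about 7 days plus 28 days, so about 35 days.

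**2. Reproduce the plan's figure.** With X1 the responses in the first 16 and X2 those in the next 30,

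P(reject) = Σ over x = 8 to 16 of P(X1 = x) · P(X2 ≥ 24 − x).

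At p = 0.40 this gives 0.0486, with a 28.4% chance of passing stage 1. At p = 0.60 it gives 0.8006. The plan says: "This design yields a type I error rate of 0.0486 and a power of 80% when the true response rate is" 60% or more. The design arithmetic is correct; the question is only who is counted.

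**3. Effect of dropping replaced patients.** Let d be the proportion of Part 1 patients at the RP2D who leave early and are replaced. The documents give no value, so d is an assumption. Take all of them as non-responders, which is the worst case. The retained six then respond with probability q = p/(1 − d), and the other 40 with probability p. Hence X1 = Bin(6, q) + Bin(10, p) and X2 = Bin(30, p). If one of seven is replaced, q = 0.40 × 7/6 = 0.467; if two of eight, q = 0.40 × 8/6 = 0.533. Exact results at a true rate of 40%:

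| Scenario | q for the six | Pass stage 1 | Type I error |
|---|---|---|---|
| No replacement | 0.400 | 28.4% | 0.0486 |
| d = 5% | 0.421 | 30.7% | 0.0535 |
| d = 10% | 0.444 | 33.3% | 0.0593 |
| 1 of 7 replaced | 0.467 | 35.8% | 0.065 |
| 2 of 8 replaced | 0.533 | 43.7% | 0.085 |

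**4. How likely replacement is.** The chance that at least one of the first six is replaced is 1 − (1 − d)^6: 27% at d = 5% and 47% at d = 10%. The chance of two or more replacements before six are retained is 1 − (1 − d)^6 (1 + 6d): about 4% and 15%.

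**5. In counts.** With one failure dropped, a passing 8/16 (50.0%) is 8/17 (47.1%) among all treated, and a rejecting 24/46 (52.2%) is 24/47 (51.1%).

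**6. If the replaced patients are not failures.** If they respond at 40% like everyone else, q stays at 0.40 and there is no bias.

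**The case against.** A reader might infer that the plan excludes replaced Part 1 patients from efficacy. It does not say so. Read literally, the references to the first 16 treated at the RP2D and the first 16 enrolled keep such patients in, and the non-response rule scores those who withdraw as failures. Six is also simply the full size of a 3+3 cohort, and the replacement text speaks of evaluability for dose tolerability. All of this stands: the defect is an ambiguity, not a stated exclusion. It does not remove the problem, because the same sections fix the six and the 10.

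Other limits also stand:

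- Patients replaced for under-dosing or a drug interaction are not thereby withdrawn and may respond, so the figures above are upper bounds.
- Section 12.3 says early withdrawals may be replaced, not that they must be.
- Patients with a DLT remain in the six.
- The early-failure route is narrow. Section 4.1 does not count prednisone at or below 0.25 mg/kg/d as failure. Its criterion for doses above that, up to 0.5 mg/kg/d, needs more than 8 weeks, longer than the window. A single dose above 0.5 mg/kg/d is a failure, but the patient may stay on treatment.
- Two of eight means 25% lost in about 35 days. For comparison, Section 3.1.6 reports 30.5% discontinued for any reason by the data cutoff in the chronic GVHD itacitinib study.

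Finally, it is tempting to say that the other 40 patients are counted from first dose. Section 12.2.3 prevents that claim: if it governs the primary endpoint, very early failures could drop out of Part 2 as well, and the contrast between the parts narrows.

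**Conclusion.** The concern holds as an unresolved conflict between two definitions of the stage 1 set, of moderate severity. It matters only if a patient treated at the RP2D in Part 1 is replaced, the six-plus-ten definition is followed, and the replaced patient would have been a non-responder. Under those conditions, type I error at a true rate of 40% is at most about 0.054–0.059 for an assumed early loss of 5–10%, 0.065 with one of seven replaced, and 0.085 with two of eight. A reader might infer that the stated 0.0486 is wrong in any event. It is not: the figure reproduces exactly and holds if nobody is replaced or if replaced patients are kept in the count.

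**What to change.** - In the study summary and Sections 4.4, 12.1 and 12.4.1, state that every patient treated at the dose declared the RP2D, including Part 1 patients replaced for DLT evaluability, counts in enrolment order toward the 16 and the 46, and is scored by the existing non-response rule.
- Let Part 2 stage 1 enrol 16 minus the number treated at the RP2D in Part 1, with the total kept at 46. If seven were treated, stage 1 enrols 16 − 7 = 9 and Part 2 enrols 9 + 30 = 39. The fixed 10 and 40 in the summary, Sections 4.4, 4.5, 12.1 and 12.4.1, including the provision for three extra patients, need matching wording.
- In Section 12.3, state that Part 1 replacement applies to the DLT evaluation only.
- Amend Section 12.2.3 so that the two-week criterion does not remove patients from the primary endpoint. Otherwise it would contradict the first change.

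This restores the stated 0.0486 and 80%. The cost is an amendment to wording, with no increase in the 46. The observed response rate may be slightly less favourable.
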